### **8.3. Lost to Follow-Up**

A patient will be considered lost to follow-up if he or she repeatedly fails to return for scheduled visits and is unable to be contacted by the study site. Site personnel are expected to make diligent attempts to contact patients who fail to return for a scheduled visit or were otherwise unable to be followed up by the site.

## 9. Study Assessments and Procedures

Section 2 lists the Schedule of Activities in [Table ITSB.1](#).

[Appendix 2](#) lists the laboratory tests that will be performed for this study. [Appendix 5](#) provides a summary of the maximum number and volume of invasive samples, for all sampling, during the study.

Unless otherwise stated in the subsections below, all samples collected for specified laboratory tests will be destroyed within 60 days of receipt of confirmed test results. Certain samples may be retained for a longer period, if necessary, to comply with applicable laws, regulations, or laboratory certification standards.

### 9.1. Efficacy and Safety Assessments

#### 9.1.1. Primary Efficacy Assessments

The primary efficacy measure is the change from baseline to Week 26 in HbA1c.

#### 9.1.2. Secondary Efficacy Assessments

The following secondary efficacy measures will be collected at the times shown in the Schedule of Activities (Section 2, [Table ITSB.1](#)).

- Prandial, basal, and total insulin doses (units and units/kg) and prandial/total insulin ratio
- Proportion of patients with HbA1c < 7.0% and < 7.5%
- SMBG 7-point profiles (fasting, 1-hour post morning meal, pre midday meal, 1-hour post midday meal, pre evening meal, 1 hour post evening meal, and bedtime)
  - 1-hour PPG excursions
  - within- and between-day glucose variability measured by the coefficient of variation and standard deviation (SD).

#### 9.1.3. Safety Assessments

- Rate and incidence of hypoglycemia:
  - documented post-dose
  - documented
  - severe
- Adverse events
- Laboratory value assessments
- Weight.

#### **9.1.4. Appropriateness of Assessments**

All efficacy and safety assessments included in this study are generally regarded as reliable and accurate with respect to diabetes mellitus.

#### **9.1.5. Study Procedures**

During this study, the patient or caregiver will be responsible for the following:

##### Every day

- Answering study diary questions for all hypoglycemia events
- Obtaining glucose value before meals and at bedtime

##### At least 3 days before all visits (telephone and office)

- Recording daily basal dose, including date
- Recording prandial doses, including date and time

##### At least 3 days during the 2 weeks before Visits 4, 10, and 15

- Collecting 3 separate 7-point SMBG profiles using the study provided meter and recording in study diary

##### **9.1.5.1. Self-Monitored Blood Glucose**

A study BG meter will be provided to all patients who meet screening criteria and should be used to obtain all 7-point SMBG values throughout the study. Patients will be required to collect glucose values at least 4 times (before meals and bedtime) each day using the BG meter provided or a personal CGM/FGM that is approved for non-adjunctive use, (i.e. results may be used to make insulin dosing decisions) per their local country regulations (Section 9.1.5.2).

Patients who do not wear a personal CGM/FGM will use the study provided BG meter;

- to perform all 4-point and 7-point glucose values,
- to record glucose values in their study diary, and
- to perform the glucose assessment for hypoglycemia events.

These glucose values are used by the investigator for dose titration as well as to assess patient safety during the study. Once BG targets are achieved and basal and prandial dose titration has been optimized, daily 4-point glucose testing frequency and timing may be adjusted at the investigator's discretion (in consultation with patient and caregiver) to allow for individual patient needs and lifestyle changes. Missing values in SMBG profiles will not be considered protocol deviations unless, in the opinion of the investigator, they are excessive and reflect noncompliance with the protocol. Patients should be encouraged to eat 3 meals on the days that the 7-point SMBG is monitored.

Patients should perform SMBG with the study provided BG meter whenever hypoglycemia is experienced or suspected (with or without symptoms), when there is perceived increased risk as related to changes in dietary intake, physical activity, or inadvertent or atypical insulin dosing. Patients who wear personal CGM/FGM should use the study provided BG meter to confirm hypoglycemia symptoms or a CGM value  $\leq 70\text{mg/dL}$  (3.9 mmol/L).

**Collection Schedule for Glucose Values**

Glucose Value	How Many	When
4-point (SMBG or CGM/FGM)	Daily	Daily
7-point (SMBG)	9 total	3× during the 2 weeks prior to Visits 4, 10, and 15.
Glucose Values		
Timing	4-Point (SMBG or CGM/FGM)	7-Point (SMBG)
Fasting (pre morning meal)	X	X
1 Hour post morning meal		X
Pre midday meal	X	X
1 Hour post midday meal		X
Pre evening meal	X	X
1 Hour post evening meal		X
Bedtime	X	X

**9.1.5.2. Use of Personal CGM or FGM**

Patients will be allowed to use their personal CGM or FGM. Patients who choose to wear their personal CGM/FGM device should make every attempt to wear it throughout the entire study. Personal CGM/FGM use (yes/no) will be recorded at Visit 4.

Patients who wear a personal CGM/FGM:

- will collect 4-point glucose values using study provided BG meter OR from the personal CGM device if approved for non-adjunctive use. BG values from a personal device are to be entered into the study diary OR investigators have the discretion to download glucose data from a personal CGM/FGM device as per usual practice
- should perform 7-point glucose values by fingerstick using study-provided BG meter, and
- should use the study-provided BG meter to confirm hypoglycemia symptoms or a CGM value  $\leq 70\text{mg/dL}$  (3.9 mmol/L).

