## 2. Schedule of Activities

**Table ITSB.1. Schedule of Activities**

	Screen a	Lead-In		Treatment Period												Safety Follow-Up	ED b
eCRF Visit Number	1	2	3 c	4	5 c	6 c	7	8 c	9 c	10	11 c	12	13 c	14 c	15	801 d	ED
Weeks from Randomization	-5	-4	-2	0	2	4	6	8	10	12	15	18	21	24	26	28	
Visit Window (±days)		3	3	3	7	7	7	7	7	7	7	7	7	7	7	7	
Informed Consent/Assent (if applicable)	X																
IWRS	X	X	X	X	X	X	X	X	X	X	X	X	X	X	X	X	X
Patient eligibility review	X	X															
Randomization				X													
Clinical Assessments																	
Demographic data e	X																
Medical history, preexisting conditions	X																
Previous diabetes therapy	X																
Record Personal CGM/FGM use (yes/no)				X													
Height f	X			X						X					X		X
Weight	X	X		X			X			X		X			X		X
Vital signs (sitting SBP, DBP, and HR) g	X	X		X			X			X		X			X		X
Concomitant medications	X	X	X	X	X	X	X	X	X	X	X	X	X	X	X	X	X
Adverse events and product complaints		X	X	X	X	X	X	X	X	X	X	X	X	X	X	X	X
Focused physical exam (including skin evaluation) h	X	X		X			X			X		X			X		X
Basal insulin dose assessment i		X	X	X	X	X	X	X	X	X	X	X	X	X	X		X
Basal insulin dose titration j		X	X	X	X	X	X	X	X	X							

	Screen a	Lead-In		Treatment Period												Safety Follow-Up	ED b
eCRF Visit Number	1	2	3 c	4	5 c	6 c	7	8 c	9 c	10	11 c	12	13 c	14 c	15	801 d	ED
Weeks from Randomization	-5	-4	-2	0	2	4	6	8	10	12	15	18	21	24	26	28	
Visit Window (±days)		3	3	3	7	7	7	7	7	7	7	7	7	7	7	7	
Prandial insulin dose assessment		X	X	X	X	X	X	X	X	X	X	X	X	X	X		X
Prandial insulin dose titration l				X	X	X	X	X	X	X							
Ancillary Supplies/Diaries/IP																	
Dispense blood glucose meter and ancillary supplies and complete training k,l		X		X			X			X		X					
Diabetes education and nutrition counseling l		X															
Dispense study diaries and complete training l		X		X			X			X		X					
Collect study diaries				X			X			X		X			X		X
Dispense IP		X		X			X			X		X					
Train on collecting 4- and 7-point SMBG profiles m		X															
Remind patient of 7-point SMBG requirements			X						X					X			

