Rate of hypoglycemic events (per patient per year) All Documented ^a Nocturnal ^a Non-Nocturnal (Documented and occurred between waking and bedtime) ^a	0-12, 0-26weeks	Negative binomial regression with treatment and age group as covariates, log (exposure/365.25 days) as the offset in the model.
Incidence of hypoglycemic events All Documented ^a Nocturnal ^a Non-Nocturnal (Documented and occurred between waking and bedtime) ^a	0-12, 0-26weeks	Logistic regression with treatment and age group as covariates.
Rate of post-dose hypoglycemic events (per patient per year) for all 3 main meals All Documented ^a	≤1, ≤2, ≤4, >4, and >2 to ≤4 hours after start of prandial insulin dose within 0-12, 0-26,weeks	Negative binomial regression with treatment and age group as covariates, log (exposure/365.25 days) as the offset in the model.
Incidence of post-dose hypoglycemic events for all 3 main meals All Documented ^a	≤1, ≤2, ≤4, >4, and >2 to ≤4 hours after start of prandial dose within 0-12, 0-26,weeks	Logistic regression with treatment and age group as covariates.
Rate of severe hypoglycemic events (per patient per 100 years)	0-12, 0-26weeks	Exposure adjusted rate 100 years (calculated by total number of events divided by total exposure for individual patients) will be provided and the empirical method (see Appendix 1 for details) will be used for treatment comparison.
Incidence of severe hypoglycemic events	0-12, 0-26weeks	Proportion of patients with severe hypoglycemia will be reported. The treatment comparison will be based on a logistic regression model with treatment and age group as covariates.

^a All documented hypoglycemia and the subcategories based on the thresholds of blood glucose ≤70 mg/dL and blood glucose <54 mg/dL will be analyzed.

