5.13.2. Subgroup Analyses for Hypoglycemic Events

For the documented hypoglycemia based on the threshold of BG ≤ 70 mg/dL, the following subgroups will be analyzed:

- age (age group 1: 1 to <12 years and 12 to <18 years, and age group 2: 1 to <6, 6 to <12, and 12 to <18 years)
- hemoglobin A1c stratum ($\leq 8.0\%$ versus $>8.0\%$)
- region
- type of basal insulin (glargine, degludec, and detemir)
- prandial insulin dosing plan (carbohydrate counting or pattern adjustment)
- personal CGM/FGM use (yes, no)

The event rate and incidence will be analyzed using the same model specified in [Table ITSB.5.4](#) with the addition of factors for subgroup, and 2-way interaction of subgroup and treatment. The 2-way interaction will be used to evaluate treatment-by-subgroup interaction.

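### Personal CGM/FGM use at Visit 4 can affect how many hypoglycemia events are documented but is in no main rate model, which gives up a little precision without causing bias

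*Protocol*

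**What the plan says.** - **Permission and recording.** Protocol 9.1.5.2: "Patients will be allowed to use their personal CGM or FGM". A patient who wears one "should make every attempt to wear it throughout the entire study". The same section says "Personal CGM/FGM use (yes/no) will be recorded at Visit 4", and the Schedule of Activities (Table ITSB.1) marks that item in the Visit 4 column only.
- **Extra meter checks.** Protocol 9.1.5.1: "Patients who wear personal CGM/FGM should use the study provided BG meter to confirm hypoglycemia symptoms or a CGM value" at or below 70 mg/dL. A patient without a device tests before meals and at bedtime, and when hypoglycemia is suspected or risk seems raised.
- **Event definition.** Protocol 9.4.1 counts a documented event from a blood glucose reading at or below 70 mg/dL, or below 54 mg/dL for the clinically significant category.
- **Randomization.** Protocol 7.2 stratifies by country, HbA1c stratum, basal insulin type and age group. Device use is not a stratum.
- **Main models.** SAP Table ITSB.5.4 gives incidence as "Logistic regression with treatment and age group as covariates". The negative binomial rate models use the same two covariates plus an exposure offset. The severe-event rate uses the covariate-free empirical method of SAP Appendix 1.
- **Subgroup.** SAP 5.13.2 lists "personal CGM/FGM use (yes, no") among the subgroups for documented hypoglycemia at the 70 mg/dL threshold, and refits the rate and incidence models with the subgroup and its interaction with treatment.

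**The concern.** From the same glucose profile, a wearer may log more meter-confirmed low values than a non-wearer, because the sensor prompts a check that would otherwise not be made. If so, Visit 4 device use predicts the event count. Leaving a baseline predictor out of a count model moves its effect into unexplained between-patient variation, and the treatment rate ratio is estimated less precisely.

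At stake is some precision in the rate part of secondary Objectives 4 (post-dose events) and 5 (documented events). The variable is already collected, so the loss is avoidable. The planned subgroup analysis does not fully recover it. It covers only the 70 mg/dL threshold, does not name the post-dose endpoints, and fits an interaction to look for effect modification rather than giving the main adjusted estimate.

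**Working it through.** **Plan's own figure.** The documents give no power or precision figure for hypoglycemia, so there is none to reproduce.

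**Inputs.** From Protocol 10.1: 283 patients randomized to each blinded arm. Assumed, because the documents give no values: mean 20 documented events per patient over 26 weeks, dispersion k = 0.8 to 1.2 within device groups, proportion of wearers q = 0.4, and detection ratio r (wearers to non-wearers) = 1.5, 2 or 3.

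**Step 1: loss of precision in the estimator.** For an omitted binary factor,

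CV² = [(1−q) + q·r²] / [(1−q) + q·r]² − 1, k′ = k + CV²(1+k), SE ratio (adjusted/unadjusted) = √[(1/20 + k)/(1/20 + k′)].

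- r = 1.5: CV² = 1.5/1.2² − 1 = 0.0417. k = 0.8 gives k′ = 0.875 and √(0.85/0.925) = 0.959. k = 1.2 gives k′ = 1.292 and √(1.25/1.342) = 0.965. Reduction 3.5-4.1%.
- r = 2: CV² = 2.2/1.4² − 1 = 0.1224. k′ = 1.020 or 1.469, and the ratio is 0.891 or 0.907. Reduction 9.3-10.9%.
- r = 3: CV² = 4.2/1.8² − 1 = 0.2963. k′ = 1.333 or 1.852, and the ratio is 0.784 or 0.811. Reduction 18.9-21.6%.

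**Step 2: what the reported interval would show.** The SAP interval comes from the standard error of a fitted negative binomial model, not from this moment formula. In simulated trials with the same inputs, fitted with and without the device term, that standard error fell by about 1-2% (r = 1.5), 4-5% (r = 2) and 9-12% (r = 3), roughly half of Step 1. The gap arises because the unadjusted model is misspecified and somewhat understates its own standard error. In simulation, its coverage was 93-95% at r = 2 and 91.5% at r = 3, against 94-95% and 94% with the term added.

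**Step 3: dependence on event rate.** Separate simulations used 283 per arm, half a year, 40% wearers and dispersion 1.0:

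| Events per patient-year | r | SE of log rate ratio, without → with | Reduction |
|---|---|---|---|
| 2 | 1.5 | 0.1207 → 0.1196 | 0.9% |
| 2 | 2 | 0.1238 → 0.1203 | 2.8% |
| 50 | 1.25 | 0.0857 → 0.0854 | 0.3% |
| 50 | 1.5 | 0.0870 → 0.0856 | 1.5% |
| 50 | 2 | 0.0898 → 0.0859 | 4.3% |

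In the last row, for an estimated rate ratio of 1, the interval exp(±1.96 × 0.0898) runs from 0.84 to 1.19 without the term. With it, exp(±1.96 × 0.0859) runs from 0.85 to 1.18. At r = 1 there is no gain.

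**Step 4: incidence and severe events.** In the same simulations, the standard error of the logistic log odds ratio did not fall when the term was added; it rose by 0.1% to 1.6%. The empirical method for the severe rate has no place for a covariate.

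**Step 5: later uptake.** Let p be baseline use and u₁, u₀ the shares of baseline non-users in each arm who start a device. Then q₁ = p + (1−p)u₁, q₀ likewise, and the rate ratio shifts by [1 + q₁(r−1)]/[1 + q₀(r−1)]. With p = 0.4, u₁ = 0.10, u₀ = 0.05, r = 1.25: 1.115/1.1075 = 1.007. With p = 0.2, u₁ = 0.20, u₀ = 0.05, r = 2: 1.36/1.24 = 1.097. These shares are assumed, and the formula treats the new users as wearing the device for the whole period.

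**The case against.** The strongest reply is that the gain is small, rests wholly on assumed inputs, and is already partly addressed. All patients, with or without a device, are asked for at least four glucose values a day and for a meter check whenever hypoglycemia is suspected, with or without symptoms. Wearers with an approved device may take the four routine values from the sensor. No passage supports a detection ratio of 2 or 3. SAP Version 3 deliberately added device use as a subgroup variable. The CGM addendum (SAP Appendix 2) compares time below 54 and 70 mg/dL across the three arms with a study sensor, though only in a subset and at two periods. The endpoints concerned carry no multiplicity control and no gated decision. All of this stands and keeps the point minor. It does not remove the case for using a baseline variable that is already collected.

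Three stronger readings are tempting, and the documents do not support them:

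- **That all the hypoglycemia intervals are wider than needed.** The gain is confined to the negative binomial rate models (Step 4). A device term would also turn the incidence odds ratio into one conditional on device use, which is a different quantity.
- **That the omission biases the treatment comparison.** Visit 4 use precedes randomized treatment and is balanced in expectation.
- **That later uptake differs by arm and would pass for a treatment effect.** Families in the open-label LY900014+20 arm know their regimen, so this is possible, but nothing in the documents suggests it. Nor is later use wholly invisible: "BG values from a personal device are to be entered into the study diary OR investigators have the discretion to download glucose data". That trace is incomplete, and no summary by arm is planned. A Visit 4 covariate would not address later uptake in any case.

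**Conclusion.** The point holds as a minor, nearly free improvement. Visit 4 personal CGM/FGM use can plausibly predict the documented event count and is absent from every main model in Table ITSB.5.4. Its omission gives up some precision in the negative binomial rate models and introduces no bias. Under the stated assumptions (20 events per patient, dispersion 0.8 to 1.2, 40% wearers), the reported interval would narrow by roughly 1-2%, 4-5% or 9-12% for detection ratios of 1.5, 2 or 3. The gain is less for rare post-dose events and nil without a detection effect. It would also be less if age group, which the simulations left out and the SAP includes, already explains part of device use. No precision benefit is claimed for the logistic incidence models or the severe-event methods.

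**What to change.** **Main change, before unblinding.** In SAP Table ITSB.5.4, add Visit 4 personal CGM/FGM use (yes/no) as a covariate to the negative binomial rate models for documented, nocturnal, non-nocturnal and post-dose events, at both glucose thresholds. At minimum, prespecify this as a sensitivity model beside the current one. Leave the severe-event methods as they are, and make no precision claim for the logistic models. Cost: one more parameter per model, on data already in the database.

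**Optional.** Repeat the yes/no item at office Visits 7, 10, 12 and 15, where glucose data are already reviewed, and tabulate it by arm. Use it descriptively only, with no adjustment for use after randomization. This would show any difference in later uptake between LY900014+20 and Humalog. Cost: a change to the Schedule of Activities and Protocol 9.1.5.2, one eCRF field at four visits, and a few minutes of site time. It helps only for visits not yet made.

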**9.2. Adverse Events**

Investigators are responsible for monitoring the safety of patients who have entered this study and for alerting Lilly or its designee to any event that seems unusual, even if this event may be considered an unanticipated benefit to the patient.

The investigator is responsible for the appropriate medical care of patients during the study.

Investigators must document their review of each laboratory safety report.

The investigator remains responsible for following, through an appropriate healthcare option, AEs that are serious or otherwise medically important, considered related to the IP or the study, or that caused the patient to discontinue the IP before completing the study. The patient should be followed until the event resolves, stabilizes with appropriate diagnostic evaluation, or is

reasonably explained. The frequency of follow-up evaluations of the AE is left to the discretion of the investigator.

Lack of drug effect is not an AE in clinical studies, because the purpose of the clinical study is to establish treatment effect.

After the informed consent form (ICF) is signed, study site personnel will record via electronic data entry the occurrence and nature of each patient's preexisting conditions, including clinically significant signs and symptoms of the disease under treatment in the study. In addition, site personnel will record any change in the condition(s) and any new conditions as AEs. Investigators should record their assessment of the potential relatedness of each AE to protocol procedure and/or IP, via electronic data entry.

The investigator will interpret and document whether or not an AE has a reasonable possibility of being related to study treatment, study device, or a study procedure, taking into account the disease, concomitant treatment, or pathologies.

A "reasonable possibility" means that there is a cause-and-effect relationship between the IP, study device and/or study procedure, and the AE.

The investigator answers yes/no when making this assessment.

Planned surgeries and nonsurgical interventions should not be reported as AEs unless the underlying medical condition has worsened during the course of the study.

If a patient's IP is discontinued as a result of an AE, study site personnel must report this to Lilly or its designee via electronic data entry, clarifying, if possible, the circumstances leading to any dosage modifications or discontinuations of treatment.

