Investigators are not obligated to actively seek AEs or SAEs in subjects once they have discontinued and/or completed the study (the patient disposition CRF has been completed). However, if the investigator learns of any SAE, including a death, at any time after a subject has been discharged from the study, and he or she considers the event reasonably possibly related to the study treatment or study participation, the investigator must promptly notify Lilly.

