#### **9.2.1.1. Suspected Unexpected Serious Adverse Reactions**

Suspected unexpected serious adverse reactions (SUSARs) are serious events that are not listed in the IB and that the investigator identifies as related to IP or procedure. United States 21 CFR 312.32, European Union Clinical Trial Directive 2001/20/EC, and the associated detailed guidances or national regulatory requirements in participating countries require the reporting of SUSARs. Lilly has procedures that will be followed for the identification, recording, and expedited reporting of SUSARs that are consistent with global regulations and the associated detailed guidances.

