5.12.4.2. Systemic Hypersensitivity Reaction

The number and proportion of patients experiencing treatment-emergent potential systemic hypersensitivity reactions will be summarized and compared by treatment group using Fisher's exact test. The following MedDRA Standardized MedDRA Query (SMQ) will be used to identify potential systemic hypersensitivity reactions from all TEAEs:

- Anaphylactic reaction (SMQ). Besides using the narrow and broad terms designated within the SMQ, the following search algorithm will also be implemented as another approach to determine if a patient had an anaphylactic reaction: if a patient (had at least 1 event in Category A) or (had at least 1 event that is in Category B and also had at least 1 event that is in Category C) or (had at least 1 event that is in Category D and [also had at least 1 event in Category B or at least 1 event in Category C])
- Angioedema (SMQ)
- Hypersensitivity (SMQ)

Specifically, need to perform the following: (1) any narrow or algorithmic term from any 1 of the 3 SMQs indicated above (ie, combined search across narrow and algorithmic portions of all 3 SMQs); (2) any narrow scope term within each SMQ, separately (ie, narrow SMQ search); (3) any term within each SMQ, separately (ie, broad SMQ search); (4) narrow scope term search within each SMQ, report the PT nested within each SMQ.

A similar summary will be provided for the TEAE related to study drug judged by the investigator.

Note that an individual patient may contribute multiple events. Also, a single event may satisfy multiple SMQs, in which case the event contributes to every applicable SMQ.

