5.15. Clinical Trial Registry Analyses

Additional analyses will be performed for the purpose of fulfilling the Clinical Trial Registry (CTR) requirements.

Analyses provided for the CTR requirements include the following:

- Summary of AEs, provided as a dataset that will be converted to an XML file. Both Serious Adverse Events and “Other” Non-Serious Adverse Events are summarized by treatment group, by MedDRA PT.
 - An AE is considered “Serious” whether or not it is a TEAE.
 - An AE is considered in the “Other” category if it is both a TEAE and is not serious. For each Serious AE and “Other” AE, for each term and treatment group, the following are provided:
 - the number of participants at risk of an event
 - the number of participants who experienced each event term
 - the number of events experienced
 - For each SAE, these additional terms are provided for EudraCT:
 - the total number of occurrences causally related to treatment
 - the total number of deaths
 - the total number of deaths causally related to treatment
 - Consistent with www.ClinicalTrials.gov requirements, “Other” AEs that occur in fewer than 5% of patients/subjects in every treatment group may be excluded if a 5% threshold is chosen. Allowable thresholds include 0% (all events), 1%, 2%, 3%, 4%, and 5%.

Adverse event reporting is consistent with other document disclosures (for example, the CSR, manuscripts, and so forth).

6. Unblinding Plan

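### Protocol Section 9.2 defines a reasonable possibility of relatedness as an existing causal relationship; applied literally, this could lower the number of events classed as related

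*Protocol*

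**What the plan says.** Protocol Section 9.2 sets the causality question in three steps.

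- The investigator documents "whether or not an AE has a reasonable possibility of being related to study treatment, study device, or a study procedure", taking account of the disease and other treatment.
- The key phrase in that question is then defined: it "means that there is a cause-and-effect relationship between the IP, study device and/or study procedure, and the AE".
- The response scale is binary: "The investigator answers yes/no when making this assessment".

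Earlier in the same section the task is described more loosely: "Investigators should record their assessment of the potential relatedness of each AE to protocol procedure and/or IP, via electronic data entry".

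Other parts of the plan then use the relatedness judgement. Section 9.2.1.1 describes SUSARs as serious events that are unlisted in the Investigator's Brochure and "that the investigator identifies as related to IP or procedure". Under Section 9.2.1, an SAE learned of after discharge must be notified if the investigator "considers the event reasonably possibly related to the study treatment or study participation". SAP Section 5.12.4.2 adds an output to the hypersensitivity tables: "A similar summary will be provided for the TEAE related to study drug judged by the investigator". SAP Section 5.15 lists, for the registry, "the total number of occurrences causally related to treatment", and a matching count for deaths.

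**The concern.** The question and its definition set different thresholds. A reasonable possibility is met when a causal link is plausible. The definition is met only when the link exists, and it contains no qualifier such as *may* or *suspected*. The answer is binary, so no middle category can hold an event that is possibly but not demonstrably related. An investigator who follows the definition must put such an event under no.

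What is at stake is how serious events are classified in a trial of patients aged 1 to under 18. Protocol Section 3.3 itself notes that pediatric data on the excipient treprostinil are limited and that its pediatric safety has not been established. In that setting, flagging an event as related should not depend on established causation.

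**Working it through.** No arithmetic applies. The check is to compare the wordings and then trace where the yes/no answer is used.

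**Step 1. The thresholds side by side**

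| Place | Threshold expressed |
|---|---|
| Protocol 9.2, recording instruction | potential relatedness |
| Protocol 9.2, the question | reasonable possibility |
| Protocol 9.2, the definition | a causal relationship exists |
| Protocol 9.2.1, SAE before IP | reasonably possibly related (to study procedure) |
| Protocol 9.2.1, SAE after discharge | reasonably possibly related (to treatment or participation) |

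Four of the five set the lower bar. The outlier is the only one that is a definition. It is current text: the amendment (b) summary in Protocol Appendix 7 lists no change to Section 9.2. No passage in either document softens or replaces it.

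**Step 2. What depends on the answer**

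- *SUSARs (Protocol 9.2.1.1).* The description rests on the investigator identifying the event as related. A no takes an unlisted serious event outside it.
- *SAEs before IP (Protocol 9.2.1).* These go to the sponsor only if judged reasonably possibly related to study procedure. This route is narrow, because it concerns procedures only.
- *SAEs after discharge (Protocol 9.2.1).* The duty to notify depends on the relatedness judgement. After a no, the sponsor might not hear of the event at all, even if it is a death.
- *AE follow-up (Protocol 9.2).* Being considered related is one of several grounds for continued follow-up.
- *Hypersensitivity (SAP 5.12.4.2).* The additional summary is restricted to events that the investigator judged related.
- *Registry (SAP 5.15).* These are the counts of causally related SAE occurrences and deaths. The SAP does not say whose judgement is counted; I assume that it is the investigator's recorded answer.

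**Step 3. What does not depend on the answer**

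- All AEs after consent are recorded (Protocol 9.2.1).
- Once IP has been received, any SAE is notified within 24 hours, whatever its relatedness (Protocol 9.2.1).
- Severe hypoglycemia is reported as an SAE whatever its cause (Protocol 9.2.1).
- The main TEAE, SAE and discontinuation tables (SAP 5.12.2) and the narratives for deaths and SAEs (SAP 5.12.8) do not select on relatedness.
- The HbA1c analyses do not use the flag.

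**Step 4. Direction and size**

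Every event that meets the definition also has a reasonable possibility of being related, but not the reverse. Literal use can therefore only lower the number of yes answers. The documents give no expected rate of related events or SUSARs and no misclassification rate, so the size of the reduction cannot be calculated.

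**The case against.** The best defence is that investigators will read the sentence in context. The question itself, the recording instruction and the two reporting rules in Section 9.2.1 all point to the lower bar, and an experienced investigator may well apply it. There are also safeguards. On-treatment SAEs reach the sponsor unconditionally. Section 9.2 asks investigators to alert the sponsor to anything that seems unusual. The sponsor states that it has its own procedures for identifying SUSARs, and an external DMC reviews safety results.

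Much of this stands. It rules out saying that related events *would* be under-reported; only *could* is supported. It also confines the problem to classification and to the conditional reports. It does not rescue the sentence. If investigators follow the definition, possible relationships are recorded as no. If they disregard it, it serves no purpose, and sites may apply different thresholds to the same field. The sponsor's SUSAR procedures are not described, so they cannot be assumed to correct the investigator's answer, and they cannot act on a post-discharge event that is never notified.

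A reader might also infer two stronger points about blinding, and neither holds. The first is that a blinded investigator can almost never assert causation. The question concerns IP, device or procedure, not treatment arm. Both blinded products are insulin lispro, so an injection-site reaction, for example, can be attributed to IP without knowing which one was given. The second is that the definition makes the open-label arm's causality judgements differ from those in the blinded arms. Knowledge of assignment could influence those judgements under any definition, and rewording this sentence would not change that.

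**Conclusion.** Wrong as written. The definition contradicts the term it defines and the neighbouring text, and nothing else in the documents corrects it. The effect can only be towards fewer events classed as related. It is limited to SUSAR identification, the two conditional SAE reporting routes, follow-up of AEs considered related, and the related-event outputs in SAP Sections 5.12.4.2 and 5.15.

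The conclusion about wording needs no assumption. The consequence rests on investigators applying the sentence literally and, for the registry counts, on those counts using the investigator's answer. A reader might infer that literal use would take related counts close to zero. The documents contain nothing from which to derive that or any other figure, so no magnitude is claimed.

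**What to change.** Replace the defining sentence in Protocol Section 9.2 with: *A reasonable possibility means that there are facts or arguments suggesting that a cause-and-effect relationship may exist between the AE and the IP, the study device or a study procedure; proof of causation is not required.* Give sites matching training so that the yes/no field is completed to one threshold. The definition then agrees with the question above it and with the reporting rules in Section 9.2.1.

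The cost is one sentence and the training. The downside is a somewhat higher count of events reported as related. No dose, clinical rule or efficacy analysis changes.
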